1.0 TRIAL OUTLINE

Study Title	Modulation of the motor pathway by Transcranial Pulse Stimulation in people with ALS: a pilot randomized trial
Study Registration	NEU-TPS-ALS-01
Study Category	Interventional Investigator sponsored study
Phase	Pilot trial
Background & Rationale	
Amyotrophic Lateral Sclerosis (ALS) is a neurodegenerative disease preferentially damaging the motor pathway, but also other cognitive networks, leading to motor paralysis and death in 3-5 years after diagnosis. At present, treatments only delay by few months the progression of the disease (e.g., to ventilatory support). For this reason, ALS is an important unmet need that would benefit from non-invasive neuromodulation therapies aimed to preserve central nervous system (CNS) networks.
 
Transcranial Pulse Stimulation (TPS) is a non-invasive neuromodulation therapy that deliver ultra-short mechanical waves of low intensity to the cortex using neuronavigation. Mechanical waves and ultrasounds modulate neuronal activity by activating mechanoreceptors on the neuronal membrane, changing neuronal excitability (producing either activation or inhibition of excitatory (glutamatergic) or inhibitory (GABAergic) neurons depending on the stimulation parameters. TPS has shown the ability to slow disease progression in patients with other neurodegenerative diseases such as Alzheimer disease and Parkinson Disease, suggesting it may protect the cortical networks from neurodegeneration.

Study Design	Adaptive trial design: Stage 1) Open label study to assess the effects (neuromodulation) of TPS on biomarkers in ALS patients; Stage 2) A randomized, blinded, sham controlled study to assess the efficacy of TPS in patients with ALS
Objective(s)	To assess the efficacy of TPS of the motor cortex on biomarkers and clinical endpoints in patients with ALS
Outcome(s)	
Primary:
 
Stage 1. Change in the motor cortex excitability threshold from baseline to week 8.
 
Stage 2. Change from baseline to month 6 in the ALS functional rating scale-revised (ALSFRS-R) total score.
 
Secondary stage 1:

	
1. Change in the motor cortex excitability (paired-pulse transcranial magnetic stimulation (ppTMS): motor evoked potential (MEP) amplitudes, resting motor threshold, intra-cortical facilitation (ICF) and short intracortical inhibition (SICI)), from baseline to week 4
 
2. Change plasma NfL levels from baseline to week 4 and 8
 
3. Changes in muscle strength, assessed by MRC sum score from baseline to week 4 and 8
 
4. Changes in hand-held dynamometry from baseline to week 4 and 8
 
Exploratory stage 1
 
1. Changes in candidate biomarkers SOD1, Ataxin 2, C9orf72, UNC13A, TDP43, stathmin 2, NfL and NfH levels in extracellular vesicles of neuronal origin (nEVs) collected from plasma from baseline to week 4 and 8
 
Secondary stage 2:
 
1. Differences (treated vs sham) and change (from baseline to end of the study (month 6)) in the slow vital capacity (SVC)
 
2. Differences (treated vs sham) and change (from baseline to end of the study (month 6)) in plasma NfL levels or other biomarkers from exploratory stage 1 if found significant
 
3. Differences (treated vs sham) and change (from baseline to end of the study (month 6)) in cortical hyperexcitability (MEP amplitudes, resting motor threshold, ICF and SICI)
 
4. Changes in muscle strength, assessed by MRC sum score from baseline to end of the study (month 6)
 
5. Changes in hand-held dynamometry, from baseline to end of the study (month 6)
 
Exploratory stage 2
 
1. Differences (treated vs sham) and change (from baseline to end of the study (month 6)) in candidate biomarkers levels in nEVs collected from plasma that were informative in stage 1 from baseline to week 4 and 8
 
Safety endpoints: presence of serious adverse events

Inclusion / Exclusion Criteria	
Inclusion: Patients with diagnosis of sporadic ALS (definite or clinically probable) as defined by the World Federation of Neurology revised El Escorial criteria, SVC of 50% or greater of estimated measure and presence of cortical hyper-excitability in the motor cortex as demonstrated by TMS; 21 to 80 years old and male or female
 
Exclusion: patients with fALS (based on medical history) that are unable to tolerate TMS studies or have a contraindication as described below

Measurements & Procedures	
 1. ALSFRS-R 2. SVC 3. MRC sum score 4. Hand-held Dynamometry 5. Motor cortex excitability by TMS 6. Plasma NfL levels 7. Blood: isolation nEVs and biomarker quantification (SOD1, Ataxin 2, C90rf72, UNC13A, TDP43, stathmin 2, NfL and NfH) 8. Brain MRI for neuronavigation 9. TPS stimulations (6 sessions of 20 min each in 2 weeks)
Study Product / Intervention	Neurolith is a medical device delivering transcranial pulse stimulations under neuronavigation guidance.
Controls	ALS patients allocated to sham stimulations. Sham treated patients will be offered to receive TPS therapy in the Open Label Extension phase (OLE) of the trial for ethical purposes.
Number of Participants & Rationale	
Stage 1: n=10
 
Stage 2: n=40 (randomization 2:1 active vs sham stimulation)
 
Rationale for sample size: this is an exploratory sample likely to be informative for experience in planning for future trials.

Study Duration:	
24 months
 
Stage 1: 6 months
 
Stage 2: 3 months recruitment, 6 months randomized phase, 6 months OLE, 3-month analysis and clinical scientific report

Timelines:	
Stage 1:
 
 ● First Patient First Visit (FPFV): September 1st, 2024 ● Last Patient Last Visit (LPLV): February 1st, 2025 
Stage 2:
 
 ● First Patient First Visit (FPFV): March 1st, 2025 ● Last Patient Last Visit (LPLV): October 1st, 2026
Study Schedule:	
Patients are recruited from the ALS center at Hospital del Mar from patients diagnosed with ALS and referrals provided by the local ALS foundation (Miquel Valls Foundation)
 
Stage 1: V1: informed consent, inclusion/exclusion criteria, TMS cortex excitability, brain MRI (for neuronavigation) can be conducted at any time between Visit 1 and 2; V2: stim; V3: TMS and biomarkers assessment week 4; V4: TMS and biomarkers assessment week 8.

	Stage 2: V1: informed consent, inclusion/exclusion criteria, TMS cortex excitability, brain MRI (for neuronavigation) can be conducted at any time between Visit 1 and 2; V2: randomization and baseline; V3-5: stim, biomarkers and scales; V6-V7: open label extension
Study Center:	ALS center and Neuromodulation center. Hospital del Mar – Pompeu Fabra University, Barcelona, Spain
Statistical Analysis Plan	Considering that this is a pilot study, and no previous data is available for this intervention, a convenience sample size of 10 subjects for the pilot and 40 patients for the randomized phase has been defined. Using the results from the CENTAUR trial ¹ in patients with ALS, a sample size of 6 patients per arm provided a 90% to detect differences by week 24 with alpha 0.05. Changes on ALSFRS-R, motor threshold, biomarker levels before and after stimulation will be assessed with ANCOVA test.

A list of abbreviations used in this document can be found in Appendix 12.3.

2.0 TRIAL DESIGN

[figure not shown]
2.1 Trial Design

This is a pilot study for evaluating the efficacy of modulating the motor cortex (M1) with Transcranial Pulse Stimulation (TPS)^{2,3} delivered by NEUROLITH device in patients with sporadic Amyotrophic Lateral Sclerosis (ALS)⁴. TPS is aimed to reduce cortical hyperexcitability and slow disease progression of the upper motor pathway, which will reduce the neurodegeneration of the lower motoneuron pathway and delay clinical progression. We will include patients with diagnosis of sporadic ALS (definite or clinically probable) as defined by the World Federation of Neurology revised El Escorial criteria, slow vital capacity (SVC) of 50% or greater of estimated measure and presence of hyperexcitability in the motor cortex as demonstrated by transcranial magnetic stimulation (TMS). Patients 21 to 80 years old and male or female are eligible. Familial ALS is excluded from the study. Clinical adverse events and therapeutic effects will be assessed during the study. Considering the primary endpoint for stage 1 is the efficacy in reducing cortical hyperexcitability, the presence of M1 hyperexcitability at inclusion (baseline) is required. The study is composed of 2 stages: stage 1 is an open label study to assess the effects of TPS on biomarkers in ALS patients (TMS based hyper-excitability and molecular biomarkers); and stage 2 is a randomized, single blinded, sham controlled study to assess the efficacy of TPS in regulatory accepted clinical scales and biomarkers in patients with ALS.

Specific procedures to be performed during the trial, as well as their prescribed times and associated visit windows, are outlined in the Trial Flow Chart - Section 6.0. Details of each procedure are provided in Section 7.0 – Trial Procedures.

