3.0 OBJECTIVE(S) & HYPOTHESIS(ES)

3.1 Co- Primary Objective(s) & Hypothesis(es)

Objectives:

Stage 1. Change in the motor cortex excitability threshold from baseline to week 8.
 Stage 2. Change from baseline to month 6 in the ALS functional rating scale-revised (ALSFRS-R) total score.

Hypothesis:

TPS stimulation delivered to M1 will decrease cortical hyper-excitability and slow disease progression.

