5.1.2 Subject Inclusion Criteria

In order to be eligible for participation in this trial, the subject must:

1. Be between 21 to 80 years of age (inclusive) on the day of signing informed consent.
2. Patients with diagnosis of sporadic ALS (definite or clinically probable) as defined by the World Federation of Neurology revised El Escorial criteria⁵, SVC of 50% or greater of estimated measure and presence of cortical hyper-excitability in the motor cortex as demonstrated by TMS.
3. Each subject must sign the informed consent form, **in accordance with local requirements**, after the scope and nature of the investigation have been explained to the subject, and before Screening assessments.
4. Based on the investigator's judgment, the subject should:
 - Be able to speak, read, and understand the language of the trial staff and the informed consent form;
 - Possess the ability to respond verbally to questions, follow instructions, and complete study assessments;
 - Be able to adhere to the stimulation protocol and visit schedules.
5. Have results of a physical examination (PE), including neurological exam and vital signs not clinically significant.
6. If female, following actively anti-conceptive measures or not be of childbearing potential as indicated by one of the following:
 - Has reached natural menopause, defined as 45 years of age with ≥6 months of spontaneous amenorrhea
 - Has had a hysterectomy;
 - Has had bilateral tubal ligation; or
 - Has had a bilateral oophorectomy (with or without a hysterectomy) and greater than 6 weeks have passed since the surgery

9. Male participants must ensure a condom is used for all sexual intercourse as well as following the acceptable methods of contraception listed above for your female partner. You must ensure that they are used for the entire duration of the study. You should not father a child or donate sperm for this same period.

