7.1.5.1.1 Visit 1: Screening, brain MRI, TMS and SVC

At Visit 1, subjects who provide informed consent will undergo a series of diagnostic and safety assessments to determine if they are eligible for the trial. A designated subject must also consent to participate and will be asked to complete certain assessments throughout the trial. Subjects planning to undergo elective procedures during the study (known prior to trial start) should not proceed until such procedures have been completed.

At the screening visit, medical history, use of drugs, alcohol, caffeine, smoking will be recorded. In addition urine test and the Columbia-Suicide Severity Rating Scale (C-SSRS) will be administered. The SVC will be collected by spirometry.

If the subject fulfills the inclusion criteria and signs the informed consent, a brain MRI and a TMS study will be scheduled in the following 2-7 days (always before Visit 2). Once obtained the brain MRI, it will be uploaded to the TPS device for neuronavigation purposes. TMS will be conducted for defining presence of hyper-excitability.

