7.1.5.1.2 Visit 2: baseline

Patients will be randomized to either treatment or sham stimulation and assigned a code (except for patient sin stage 1, which are not randomized, and all receive active stimulation). Before starting stimulation, the researcher will conduct a vital signs, physical exam and neurological examination. Urine (50 ml) and blood (20 ml) will be collected and stored. Then, the patient will be subjected to the first TPS stimulations (a 20 min stimulations).

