8.9 Sample Size and Power Calculations

Sample size

This study will recruit 10 patients for stage 1 (open label) and 40 patients for stage 2 (randomized DBP). Using the results from the CENTAUR trial¹ in patients with ALS, a sample size of 6 patients per arm provided a 90% to detect differences by week 24 with alpha 0.05.

Power for the primary hypothesis

Considering that this is a pilot study, and no previous data is available for this intervention, a convenience sample size of 10 subjects for stage 1 and 40 for stage 2 has been defined. Using the results from the CENTAUR trial¹ in patients with ALS, a sample size of 6 patients per arm provided a 90% to detect differences by week 24 with alpha 0.05.

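### Stage 1 does not separate the TMS that qualifies a patient as hyperexcitable from the TMS that serves as baseline, so regression to the mean could favour TPS in the uncontrolled primary change score

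*Protocol*

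**What the plan says.** Stage 1 has no comparison group. Section 7.1.5.1.2 assigns Visit 2 patients to treatment or sham, "except for patient sin stage 1, which are not randomized, and all receive active stimulation". Section 8.9 sets the size: "This study will recruit 10 patients for stage 1 (open label". The primary endpoint in section 3.1 is "Stage 1. Change in the motor cortex excitability threshold from baseline to week 8".

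Entry depends on the same domain. Inclusion criterion 2 in section 5.1.2 asks for "presence of cortical hyper-excitability in the motor cortex as demonstrated by TMS", with no TMS parameter and no cut-off. Section 2.1 gives the reason, namely that reducing hyperexcitability is the Stage 1 primary endpoint, and writes "the presence of M1 hyperexcitability at inclusion (baseline) is required".

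The TMS before treatment is placed differently in different sections:

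- Section 1.0, Study Schedule, puts it at Visit 1: "V1: informed consent, inclusion/exclusion criteria, TMS cortex excitability". Visit 2 is listed as stimulation only. The next TMS readings are at weeks 4 and 8.
- Section 7.1.5.1.1 schedules it after consent and always before Visit 2, for one stated purpose: "TMS will be conducted for defining presence of hyper-excitability".
- The Stage 1 flow chart in section 6.0 ticks TMS once, in the Visit 2 (Baseline) column. The Stage 2 chart ticks it at both Screen and Rand Base.
- Section 7.1.5.1.2 lists what is done at Visit 2 before the first stimulation and does not mention TMS.

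**The concern.** A reading that is high enough to pass a cut-off is, on average, partly high by chance. If the change score starts from that same reading, the next one will tend to be closer to normal without any treatment. In Stage 1 this drift goes in the direction of the study hypothesis, which is reduced hyperexcitability, and no sham arm shares it. The ANCOVA named in Table 5 does not help: without a comparison group, adjusting at the sample's own baseline mean leaves the mean change as it was. A purely descriptive mean change carries the same bias.

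Stage 2 is less exposed. Both randomised arms regress alike, so the active-versus-sham contrast is protected.

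**Working it through.** **Step 1. Count the TMS sessions before treatment in Stage 1.** The synopsis gives one, section 7.1.5.1.1 gives one, and the Stage 1 chart gives one. No single section schedules two. The chart's one TMS tick is in the same Visit 2 column as its one brain MRI tick. Section 7.1.5.1.1 places both the MRI and the TMS before Visit 2, so the chart's tick is probably that same session. Two sessions arise only if section 7.1.5.1.1 and the chart are taken to describe different ones.

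**Step 2. Expected change with no treatment effect, if one reading serves both roles.** The protocol gives no figure for TMS repeatability, the cut-off or the pass rate, and no power or SD for Stage 1, so there is no plan figure to reproduce. Inputs:

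- n = 10 (section 8.9).
- Assumed: share of screened patients who pass, p = 0.3 to 0.9.
- Assumed: test-retest correlation, ρ = 0.5 to 0.9.
- Assumed: entry and endpoint use the same TMS parameter, and readings are bivariate normal.

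With c the cut-off that a share p exceeds and φ the normal density, the spurious improvement in SDs of the screened population is

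(1 − ρ) × φ(c) / p.

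The factor φ(c)/p is 1.159 at p = 0.3, 0.798 at p = 0.5, 0.497 at p = 0.7 and 0.195 at p = 0.9. For example, p = 0.5 and ρ = 0.6 give 0.4 × 0.798 = 0.32 SD, and p = 0.9 and ρ = 0.8 give 0.2 × 0.195 = 0.04 SD.

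**Step 3. Chance of a significant improvement.** This was simulated with 40,000 trials per cell, a paired t-test and two-sided 5%, counting only results in the direction of benefit (nominal 2.5%). Each cell shows the spurious shift and then the rejection rate.

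| Share passing | ρ = 0.5 | ρ = 0.6 | ρ = 0.7 | ρ = 0.8 | ρ = 0.9 |
|---|---|---|---|---|---|
| 30% | 0.58 SD, 44% | 0.46 SD, 35% | 0.35 SD, 27% | 0.23 SD, 19% | 0.12 SD, 11% |
| 50% | 0.40 SD, 23% | 0.32 SD, 19% | 0.24 SD, 15% | 0.16 SD, 11% | 0.08 SD, 7.5% |
| 70% | 0.25 SD, 11% | 0.20 SD, 10% | 0.15 SD, 8% | 0.10 SD, 6.5% | 0.05 SD, 5% |
| 90% | 0.10 SD, 4% | 0.08 SD, 4% | 0.06 SD, 4% | 0.04 SD, 4% | 0.02 SD, 3% |

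The range quoted in the conclusion, about 4% to 35%, takes ρ from 0.6 to 0.8 and p from 0.3 to 0.9.

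**Step 4. If entry and endpoint use different parameters.** Let X be the entry parameter and Y the endpoint parameter, at occasions 1 and 2. The spurious improvement in Y is then [corr(X1, Y1) − corr(X1, Y2)] × φ(c)/p. It is zero if measurement errors of X and Y in one session are independent, and positive if they share error. This matters because section 5.1.2 names no parameter, section 3.1 speaks of a threshold, section 7.1.2.2.3 makes SICI the primary criterion for change, and Table 5 analyses motor threshold.

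**Step 5. With a second reading before treatment as baseline, not used for selection.** The same simulation gives a mean spurious change of 0.00 SD and a two-sided error of 0.048 to 0.052 in every scenario.

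**The case against.** The strongest reply is that the protocol does contain two sessions: an eligibility TMS before Visit 2 (section 7.1.5.1.1) and a baseline TMS ticked at Visit 2 (flow chart). On that reading, the word baseline in section 2.1 marks a point in time and does not name a measurement. This cannot be excluded. A reader might infer that the protocol fixes one shared reading; the documents do not go that far. They leave the matter open, with the wording of section 2.1 and the synopsis pointing toward one reading.

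The Stage 1 chart is also weak evidence of a deliberate single TMS. It stops at week 4 and shows no TMS after treatment, although the synopsis requires readings at weeks 4 and 8. Nor does the silence of section 7.1.5.1.2 prove much, since its list also omits ALSFRS-R, MRC score and dynamometry, all charted at Visit 2. Both points stand.

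A reader might also take the error rates above as the protocol's false-positive risk. They are not. They rest on assumed pass rates and repeatability, on a common parameter, and on a paired t-test that the protocol does not name; section 8.1 says the results will be descriptive only. Nor is any Stage 1 TMS result stated to decide whether Stage 2 proceeds.

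What remains is that the bias, where present, lies in the mean change itself and always points toward TPS. A later analysis plan cannot supply a baseline reading that was never taken.

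**Conclusion.** The point holds as an unresolved ambiguity with a one-sided consequence. The protocol does not separate the qualifying TMS from the baseline TMS in Stage 1, and section 2.1 equates them. If one reading does both jobs, the uncontrolled primary change is biased toward a TPS effect.

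The size cannot be determined from the documents. It is small if nearly all screened patients qualify, or if entry and endpoint rest on different TMS parameters with little shared error. It is material if the cut-off excludes many patients and repeatability is moderate: about 4% to 35% false significant improvement against 2.5%, under the assumptions set out above. Natural progression over eight weeks could add to or offset it, and cannot be separated without a control.

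This should be fixed because it touches the Stage 1 primary endpoint and the remedy is cheap. It does not invalidate the randomised comparison in Stage 2.

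**What to change.** 1. Section 7.1.5.1.1: state that the screening TMS is used for eligibility only.
2. Sections 3.1 and 7.1.5.1.2: define the Stage 1 baseline as the Visit 2 TMS already ticked in the flow chart, completed before the first stimulation, and add TMS to the list of procedures before stimulation.
3. State that the Visit 2 TMS value cannot be used to exclude a patient. Section 7.1.1.2 withdraws patients who fail criteria at visits, and section 7.1.1.9 confirms eligibility at Visit 2. Unless these are reconciled, selection on the baseline reading, and with it the bias, would persist.
4. Section 2.1: delete the bracketed word baseline. Section 6.0: tick TMS at Screen in the Stage 1 chart, and align the synopsis.
5. Name one TMS parameter consistently in sections 3.1 and 7.1.2.2.3 and in Table 5, and give the parameter and cut-off for entry in section 5.1.2.
6. Report the Stage 1 change as uncontrolled.

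The cost is wording, one tick in the chart, and at most one repeat non-invasive TMS in 10 patients. There is no extra TMS if the session in section 7.1.5.1.1 and the charted Visit 2 session are already separate.

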2.2 Trial Diagram

The trial design is depicted in [Figure 1](#).

Stage 2: TPS Efficacy study ALS

[figure not shown]

Figure 1 Trial Design Diagram

3.0 OBJECTIVE(S) & HYPOTHESIS(ES)

3.1 Co- Primary Objective(s) & Hypothesis(es)

Objectives:

Stage 1. Change in the motor cortex excitability threshold from baseline to week 8.
 Stage 2. Change from baseline to month 6 in the ALS functional rating scale-revised (ALSFRS-R) total score.

Hypothesis:

TPS stimulation delivered to M1 will decrease cortical hyper-excitability and slow disease progression.

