6.0 TRIAL FLOW CHART

Table 3 Trial flow chart

Stage 1 Visit Number	1	2	3-5	6
Visit Title	Screen	Baseline	Stimulation	End
Scheduled Week	0	1	2-3	4
Scheduling Window by Days:	3	3	2	5
Administrative Procedures				
Informed Consent	X			
Inclusion/Exclusion Criteria	X			
Identification Card	X			
Medical History	X			
Prior Medication Review	X			
Monitor Trial Device Compliance		X	X	
Clinical Procedures Assessments				
TPS stimulations	X	X	X	
Vital Signs		X	X	X
Physical Exam		X	X	X
MRC sum score		X	X	X
Hand-held dynamometry		X	X	X
Brain MRI		X		
TMS		X		
Neurological examination	X	X	X	X
C-SSRS	X	X	X	
ALSFRS-R	X	X	X	X
Blood draw		X	X	X
SVC		X		

Stage 2 Visit Number	1	2	3-5	6-7	8	9	10-16	17-18	19
Visit Title	Screen	Rand Base	Stim	Stim FU	End DBP	Onset OLE	Stim 3	Stim FU	End OLE
Scheduled Week	0	1	2-3	8-16	16	16	16-18	26-34	34
Scheduling Window by Days:	3	3	2	2	5	7	2	2	5
Administrative Procedures									
Informed Consent	X								
Inclusion/Exclusion Criteria	X								
Identification Card	X								
Medical History	X								
Prior Medication Review	X								
Monitor Trial Device Compliance		X	X	X			X	X	
Clinical Procedures Assessments									
TPS stimulations	X	X	X	X			X	X	
Vital Signs		X	X	X	X	X	X	X	X
Physical Exam		X	X	X	X	X	X	X	X
MRC sum score		X	X	X	X	X	X	X	X
Hand-held dynamometry		X	X	X	X	X	X	X	X
Brain MRI	X								
TMS	X	X	X	X	X				
Neurological examination	X	X	X	X	X	X	X	X	X
C-SSRS	X	X	X	X			X	X	
ALSFRS-R	X	X	X	X	X	X	X	X	X
Blood draw		X	X	X	X				
SVC		X				X			

Stim: TPS stimulation (6 times in 2 weeks, 20 min each); rand: randomization; Base: baseline; DBP: double blind period; OLE: Open Label Extension

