7.1.5 Visit Requirements

Visit requirements are outlined in Section 6.0 - Trial Flow Chart. Specific procedure-related details are provided above in Section 7.1 - Trial Procedures.

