7.1.5.1 Visits

Each visit should be performed as noted in the Trial Flow Chart. For visits that require additional explanations, please see those specific visits below.

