7.1.5.1.3 Visit 3-5, 6-12, 15-21 and 22-28: stimulation visits

At each visit the patient will be reassessed for vital signs, physical exam and neurological exam. After the completion of each 6-session period, the C-SSRS will be administered. Blood and urine will be collected the last day of stimulation for each 6-session period. TMS and ALSFRS-R will be assessed the last day of stimulation for each 6-session period.

7.1.5.1.2 Visit 13, 14 and 29: end of stage 1, end of DBP, onset and end of OLE of stage 2

During such visits, vital signs, physical exam, and neurological exam and ALSFRS-R will be conducted.

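### The Stage 1 primary endpoint needs TMS at week 8, as the synopsis plans, but the Stage 1 flow chart stops at week 4 with TMS at baseline only; the primary TMS measure is also named in conflicting ways

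*Protocol*

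**What the plan says.** **Endpoint.** Section 3.1 gives the Stage 1 primary as "Stage 1. Change in the motor cortex excitability threshold from baseline to week 8". Sections 1.0, 8.1 (Table 5) and 8.4.1 give the same endpoint. Section 3.2 adds motor cortex excitability at week 4, and plasma NfL, MRC sum score and hand-held dynamometry at weeks 4 and 8. Section 3.3 adds the nEV biomarkers at weeks 4 and 8.

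**Synopsis schedule.** Section 1.0 plans four Stage 1 visits, the last two being "V3: TMS and biomarkers assessment week 4; V4: TMS and biomarkers assessment week 8".

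**Flow chart.** The Stage 1 chart in Section 6.0 has the header row "Scheduled Week 0 1 2-3 4", for screening, baseline, stimulation and end. There is no later column. The TMS row carries one mark, at Visit 2 (baseline).

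**Which schedule applies.** Section 2.1 says of the procedures that "their prescribed times and associated visit windows, are outlined in the Trial Flow Chart". Section 7.1.5 says "Visit requirements are outlined in Section 6.0". Section 7.1.5.1 says "Each visit should be performed as noted in the Trial Flow Chart" and then "For visits that require additional explanations, please see those specific visits below".

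**Visit text.** Section 7.1.5.1.1 places a TMS between Visits 1 and 2 to establish hyperexcitability. Section 7.1.5.1.3 says "TMS and ALSFRS-R will be assessed the last day of stimulation for each 6-session period". The text for the end of Stage 1 lists vital signs, physical and neurological examination and ALSFRS-R, but no TMS.

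**Measure.** The endpoint speaks of an *excitability threshold*. The analysis sentence in Sections 1.0 and 8.1 speaks of *motor threshold*. Section 7.1.2.2.3 records four measures (MEP amplitude, resting motor threshold, ICF, SICI) and makes SICI the primary criterion for a treatment-related change in excitability. Sections 2.1 and 4.2.3.1 describe the primary without naming a parameter.

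**The concern.** The part of the protocol that staff are told to work from does not contain the measurement that the Stage 1 primary endpoint needs. A statistical analysis plan cannot repair this, because it cannot recover a visit that did not take place. Stage 1 has 10 participants and Section 5.9 allows no replacement, so following the chart would leave the primary endpoint empty for everyone.

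The loss would carry into Stage 2. Sections 3.2 and 3.3 let Stage 1 biomarker results decide which biomarkers are taken forward, and half of the planned post-baseline biomarker times (week 8) have no chart visit.

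The measure is a smaller matter. Resting motor threshold and SICI are listed as separate quantities. As written, either could be reported as the Stage 1 primary after the data are seen, with a protocol section to cite for it.

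**Working it through.** No sample size or power figure is involved. The check sets the schedules side by side and does calendar arithmetic on the chart.

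**1. Stage 1 TMS by source**

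| Source | Before or at baseline | After baseline |
|---|---|---|
| Flow chart, Section 6.0 | Visit 2 (week 1) | none |
| Visit text, Section 7.1.5.1 | between Visits 1 and 2 | last stimulation day |
| Synopsis, Section 1.0 | V1 | weeks 4 and 8 |
| Endpoints, Sections 3.1 and 3.2 | baseline | weeks 4 and 8 |

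The chart and visit text together cover 0 of the 2 TMS endpoint times.

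**2. Calendar arithmetic**

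Assumptions: day = 7 × chart week, so screening is day 0 and baseline day 7; windows are plus or minus. No section says whether weeks 4 and 8 count from screening or baseline, so both are shown.

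- Last chart visit: 4 × 7 = day 28; with the 5-day window, 28 + 5 = day 33.
- Week 8 from screening: 8 × 7 = day 56. Gap: 56 − 33 = 23 days.
- Week 8 from baseline: 7 + 56 = day 63. Gap: 63 − 33 = 30 days. With the 3-day baseline window (day 4 or 10): 60 − 33 = 27 to 66 − 33 = 33 days.
- Last TMS from the visit text, at the end of chart weeks 2-3: 3 × 7 = day 21; with the 2-day window, day 23.
- From that TMS to week 4: 28 − 23 = 5 days (screening origin) or 35 − 23 = 12 days (baseline origin).
- From that TMS to week 8: 56 − 23 = 33 days or 63 − 23 = 40 days.

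**3. Other week-8 endpoints**

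Plasma NfL, nEV biomarkers, MRC sum score and dynamometry: 0 of 4 have a chart visit at week 8. Section 7.1.3.1 does not fill the gap for NfL. Its times are baseline, after each stimulation session, end of the double-blind period and end of the extension, and Stage 1 has neither of those periods.

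**4. Week-4 endpoints other than TMS**

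If weeks count from screening, the End visit covers all four. If they count from baseline, it falls 28 − 7 = 21 days after baseline against a target of 28. Its latest date is 33 − 7 = 26 days after a day-7 baseline, and 33 − 4 = 29 days only if baseline was also 3 days early.

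**5. Visit numbers**

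The end-of-stage text is headed Visits 13, 14 and 29. Stage 1 has Visits 1-6 in the chart and V1-V4 in the synopsis, so staff cannot use that heading to find the missing visit.

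**6. Size of the measure problem**

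Illustration only: if two independent measures were each tested at 0.05, the chance of at least one false positive would be 1 − 0.95² = 9.75%. The two measures are probably not independent, so this only shows the order of magnitude.

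**The case against.** The strongest reply is that the week-8 measurement is planned: the synopsis schedules it outright and every statement of the primary endpoint names week 8. No section expressly ranks the chart above the synopsis, and the design figures cannot be seen in the text at hand. On this reading the chart is simply out of date, and attentive staff would follow Section 1.0. That is fair, and the finding is a contradiction, not an unplanned primary. It does not remove the problem. Three sections send the reader to the chart for visit times, and none sends the reader to the synopsis. A lost mark in the text could explain one missing TMS, but not a missing week-8 column.

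Some of the day counts are softer than they look. Section 7.1.5.1.3 counts Visits 6-12 as stimulation visits although Visit 6 is the Stage 1 end visit in the chart, and the chart shows four visits (2 and 3-5) for six sessions. The date of the last stimulation-day TMS is therefore nominal. The 23- and 30-day gaps do not depend on it.

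On the measure, Section 7.1.2.2.3 does name a parameter, so the fault is conflicting wording, not silence. Section 8.1 also says results will be descriptive only, which limits the harm from a late choice, although Table 5 in the same section names ANCOVA. This part alone would be a minor point.

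The 100 ml blood total in Section 7.1.3.2 is no error in itself: the Stage 1 chart has five draw visits, and 5 × 20 = 100 ml. It needs attention only once a draw is added.

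**Conclusion.** The concern holds and must be fixed. The Stage 1 chart and visit text contradict the synopsis and the primary endpoint. Followed as written, they give no TMS at week 4 or week 8 and no visit for the four other week-8 endpoints. Week 8 lies 23 days (screening origin) or 30 days (baseline origin) beyond the last visit window, assuming 7-day chart weeks and windows read as plus or minus. The conclusion is the same under either origin. The schedule conflict carries the severity. The conflict between threshold and SICI is real and should be settled in the same amendment, but it is secondary.

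**What to change.** Amend the protocol before any Stage 1 data are seen:

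- **Chart (Section 6.0, Stage 1).** Reconcile it with the synopsis and endpoints: TMS and blood draw at week 4 and at a week-8 end visit, with MRC sum score and dynamometry also at week 8 as Section 3.2 requires. The stimulation schedule is not part of this change.
- **Week origin.** State whether weeks count from screening or baseline. If from baseline, re-date the week-4 visit to match.
- **Visit text (Section 7.1.5.1).** Give Stage 1 its own text with visit numbers that match the chart. The Stage 2 and extension texts need not change for this point.
- **NfL (Section 7.1.3.1).** Give the Stage 1 times as baseline, week 4 and week 8, plus any post-stimulation draws that are kept.
- **Blood volume (Section 7.1.3.2).** State which stage the total covers and update it. Adding one draw to the five in the Stage 1 chart gives 6 × 20 = 120 ml.
- **Primary measure.** Name one TMS parameter in identical words in Sections 1.0, 3.1, 4.2.3.1, 7.1.2.2.3, 8.1 and 8.4.1, and make the other TMS parameters secondary.

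**Cost.** Against the synopsis, this is wording plus the two week-8 strength assessments, which its schedule line does not mention. Against the chart, each participant gains one full visit (TMS, a 20 ml draw, MRC sum score and the 16-muscle-group dynamometry) and a TMS at week 4. For 10 participants that is 10 more visits and 10 × 2 = 20 more TMS sessions.
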